13.3 Measures to Minimize Bias

We will use block randomization, ensuring that equal numbers of subjects are randomized to each group. For this two-arm balanced-design study, the randomization will consist of blocks of patients randomly assigned (allocation ratio of 1:1) to ifetroban or placebo. Matching capsules of ifetroban and placebo will be supplied by Cumberland Pharmaceuticals and provided to the BWH Investigational Drugs Services pharmacy (IDS) for storage and distribution. The IDS will conduct the randomization and keep records to maintain study blinding.

Laboratory analyses (flow cytometry, cellular assays, eicosanoid measurement, etc.) as required for any secondary and exploratory outcomes will also be performed in a blinded fashion, as along with the clinical staff, laboratory staff will also be blinded during the study.

13.4 Analysis Plan

13.4.1 Analysis Populations.

N/A

13.4.2 Primary Analysis of Primary Outcome

To power for a change in the PD_2 , we will use a two-sided two-sample t-test for mean difference with unequal variance, comparing the difference between treatment with ifetroban and placebo. Based on our current internal clinical data, we estimate an average PD_2 of 60, with a standard deviation of 42. Assuming this standard deviation to remain true, with a sample size of 20 patients per treatment arm, we will have 83% power to detect a 3-fold shift in PD_2 (or an average an increase in PD_2 to 180 for patients on ifetroban, with a standard deviation of 170), at a 0.05 level of significance.

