2. Before aspirin is given, a urine sample will be collected for pregnancy and eicosanoid metabolites, and a nasal fluid and nasal epithelial scraping sample will be taken, along with a blood draw for CBC/differential and cellular assays.
3. Subjects will then undergo an oral aspirin desensitization procedure. They will receive an initial 40.5 mg dose of aspirin, and then every 90 minutes will be given increasing doses of 81, 162, and 325 mg aspirin.
4. Vital signs are obtained every 90 minutes during the aspirin challenge/desensitization.
5. If at any point the subject develops symptoms of a reaction, we will examine them and record the time of onset of reaction. The dose of reaction that induces an increase in TNSS of 2 or more points will be recorded as the provocative dose.
6. Following the onset of reaction, patients will be observed for a 3-hour period, during which time no more aspirin doses will be given. TNSS will be recorded at the onset of reaction and again every 30 minutes during this 3-hour period after reaction.
7. Pulmonary function testing is repeated before each dose and at the onset of reaction and if it remains within 85% of their pre-challenge FEV₁, it will be repeated every 90 minutes during the 3-hour period after reaction. If the FEV₁ falls by 15% or more from their morning pre-challenge FEV₁, they will be treated with

MDI albuterol (up to 8 puffs per administration), followed by nebulized albuterol if needed and FEV₁ will be repeated every 30 minutes until it has returned to within 85% of their morning pre-challenge FEV₁.

8. No medications (except albuterol and ipratropium) will be used for relief of symptoms during the desensitization until the 3-hour period of observation following onset of reaction is completed, unless required for a patient's safety.
9. A blood sample will be collected 1 hour after the onset of reaction for CBC/differential, platelet activation assays, and platelet-leukocyte aggregate measurements. Urine and nasal fluid samples will be collected 90 minutes after the onset of reaction, or if there is no clinical reaction at all, will be collected 90 minutes after the 325mg dose of aspirin is given.

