13.7 Sample Size Considerations

Assuming that there will be a dropout rate of 10-20%, we will seek to recruit 50 individuals with suspected AERD from our new referrals to meet a target sample size of 40 to complete the study, with 20 in each treatment arm. We will enroll additional subjects if we have an unusually high dropout rate. As detailed in section 13.4.2, with this sample size of 20 patients per treatment arm, we will have 83% power to detect a 3-fold shift in PD₂ (or an average an increase in PD₂ to 180 for patients on ifetroban, with a standard deviation of 170), at a 0.05 level of significance.

13. Identification and Access to Source Data**13.1. Source Data**

The Principal Investigator will keep accurate records to ensure that the conduct of the study is fully documented. Data derived from source documents will be transferred to protocol-specific CRFs. Hard copy results of the following clinical evaluations and clinical laboratory evaluations will be maintained in the participant's protocol-specific binder, housed at the Asthma Research Center:

- Patient medical histories, concomitant medications, adverse event forms (results written onto CRF)
- CBC/differential (printed copy)
- PFTs (printed copy)
- FeNO (results written onto CRF by coordinator/investigator)
- Pregnancy test (results written onto CRF by coordinator/investigator)
- Physical exam (results written onto CRF by coordinator/investigator)
- Patient questionnaires (results written onto CRF by patient)
- Details of which biologic specimens collected at each visit (written onto CRF by coordinator/investigator)

The applicable clinical study data will be transferred to a password-secured REDCap database on a dedicated server.

Data derived from research laboratory evaluations (flow cytometry, eicosanoid and cytokine levels, cellular assays) will be stored as a hard copy (as applicable) within laboratory notebooks, or within the appropriate assay-specific software program as required for each type of analysis.

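### The ifetroban SD of 170 behind the 83% power is larger than PD2, as defined, can have with a mean of 180; its source and the PD2 rule for non-reactors need stating

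*Combined protocol and SAP*

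**What the plan says.** Section 13.4.2 names the test: "we will use a two-sided two-sample t-test for mean difference with unequal variance". From internal data, "we estimate an average PD_2 of 60, with a standard deviation of 42". It continues with "Assuming this standard deviation to remain true" and then, within the same sentence, sets the ifetroban mean and SD: "to 180 for patients on ifetroban, with a standard deviation of 170), at a 0.05 level of significance". The result is 83% power. Section 13.7 carries the figure into the sample size: "with this sample size of 20 patients per treatment arm, we will have 83% power". The 60 and the 42 are attributed to internal data; no source is given for the 170.

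Sections 3.2 and 13.2 define PD2 by interpolating, on the log dose scale, between the dose before the reaction and the dose that provoked it. Sections 3.1 and 8.3 start the challenge at 40.5 mg, after which subjects "will be given increasing doses of 81, 162, and 325 mg aspirin". Both record as provocative the dose at which TNSS has risen by 2 or more. Both also foresee subjects who do not react at all and say when to sample them, but no section gives those subjects a PD2.

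**The concern.** The SD assumed for the ifetroban arm looks too large for the endpoint it describes. A variable confined to a range, with its mean fixed, has a largest possible SD, and 170 lies above that limit for PD2 as written. The 83% is the only justification given for 20 per arm.

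The direction of any error in power matters less than what the mismatch suggests: the PD2 used for planning may not be the PD2 in sections 3.2 and 13.2. If ifetroban blunts reactions, as hypothesised, subjects without a reaction could gather in the ifetroban arm. Whatever value they receive would then drive that arm's mean and SD and the t-test. If such a value was used in planning but never written down, part of the primary endpoint is unspecified.

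**Working it through.** **Inputs.** Two-sided alpha 0.05, unequal-variance (Welch) t-test, 20 per arm, placebo mean 60 and SD 42, ifetroban mean 180 and SD 170 (13.4.2, 13.7). Challenge doses 40.5, 81, 162 and 325 mg; provocative dose defined by a TNSS rise of at least 2 (3.1, 8.3). PD2 formula (3.2, 13.2).

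**Step 1: reproduce the 83%.**
- Standard error = sqrt(42²/20 + 170²/20) = sqrt(88.2 + 1445) = 39.16.
- Noncentrality = (180 − 60)/39.16 = 3.06.
- Satterthwaite df = (88.2 + 1445)² / (88.2²/19 + 1445²/19) = 21.3.
- Power from the noncentral t = 83.2%. The stated figure reproduces.

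**Step 2: the range of PD2.** The formula moves from log PrevDose towards log ProvocDose by the fraction (2 − previous rise)/(maximum rise − previous rise). Before the provocative dose the rise is below 2, because otherwise the earlier dose would have been provocative. At the provocative dose it is at least 2. The fraction is therefore above 0 and at most 1, and PD2 lies above PrevDose and at or below ProvocDose. The highest ProvocDose is 325 mg.

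**Step 3: the largest possible SD.** For a variable between a and b with mean m, the maximum SD is sqrt((m − a)(b − m)). Take the most generous floor, a = 0, with b = 325 and m = 180: sqrt(180 × 145) = 161.6. Read as a sample SD with divisor n − 1 at n = 20, the limit is 161.6 × sqrt(20/19) = 165.8. Both are below 170.

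**Step 4: power within the range.** Means 60 and 180, placebo SD 42, 20 per arm, same Welch calculation:

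| Ifetroban SD | Power |
|---|---|
| 170 (as stated) | 83.2% |
| 161.6 (limit, floor 0) | 86.6% |
| 126 | 97.2% |
| 100 | 99.7% |

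Data at the limit are far from normal (every value 0 or 325). A simulation of that extreme case, with bounded placebo data, gives 86.2%, so the normal-theory figure is close.

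**Step 5: what would make 170 attainable.** Solve (180 − 0)(b − 180) = 170²: b = 180 + 28,900/180 = 340.6 mg. With a floor of 40.5 mg, b = 180 + 28,900/139.5 = 387.2 mg. Some PD2 values must therefore exceed about 341 mg.

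**Step 6: power if values above 325 mg are in use.** The documents give no such values, so these SDs are assumptions, with the means held at 60 and 180: SD 180 gives 79%, SD 200 gives 71%. For a cap near 650 mg the mathematical maximum SD is about 257 (floor 40.5) to 291 (floor 0), giving about 50% to 41%. That is an outer bound, not an expectation.

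**The case against.** **The calculation is right and errs on the safe side.** This stands. The fault lies in one planning input. A reader might infer that the 83% is miscalculated or that the trial is underpowered. The documents support neither: 83.2% follows from the stated inputs, and every SD attainable within 0 to 325 mg gives more power.

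**An SD of 170 is not impossible on every reading.** This stands too. The formula itself contains no cap. If a subject counted as reacting on FEV₁ alone (5.4), with a TNSS rise of only 1 after 325 mg and none before, the formula would extrapolate to 325²/162 = 652 mg. A value assigned to non-reactors, or a cumulative dose scale (40.5 + 81 + 162 + 325 = 608.5 mg), would also allow 170. However, the rise of at least 2 required in 3.1 and 8.3 argues against the first. No section contains the second. The formula's dose definitions and the dose coding in 3.3 use single doses, which argues against the third.

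**A tighter limit is tempting.** Taking 40.5 mg as the floor gives a maximum SD of sqrt(139.5 × 145) = 142.2 and power of 93.3%. The documents do not support that floor. A subject who reacts at 40.5 mg has no previous dose, so the formula returns nothing, and no rule fills the gap. Section 5.4 says that most reactions occur at 81 mg or below, so first-dose reactors cannot be set aside. The defensible limits are 162 and 86.6%.

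**The wording about the SD remaining true.** A reader might take this as saying that 42 applies to both arms, which would give power above 99.9%. The same sentence gives 170 for ifetroban and the section specifies unequal variances, so the natural reading is that 42 is the placebo SD. It is loose drafting, not a second error.

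**Conclusion.** The ifetroban SD of 170 does not fit PD2 as sections 3.2, 8.3 and 13.2 define it; with mean 180 the SD is at most about 162. If PD2 is limited to 325 mg, the stated 83% understates power by at least about 3.5 percentage points (86.6% against 83.2%), and the sample size needs no change on this account. If the 170 reflects an unwritten value above 325 mg or another dose scale, the endpoint definition is incomplete. Power could then be higher or lower than 83%, and the adequacy of 20 per arm is open until that rule is known.

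This rests on the planned means of 60 and 180, on the placebo SD of 42, and on applying the formula only where TNSS rises by at least 2 by 325 mg. Which of the two explanations is true cannot be settled from the documents.

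**What to change.** - State the source of the 170 in 13.4.2.
- If PD2 is limited to 325 mg, restate the ifetroban SD (at most about 162) and the power (at least about 87% by the same Welch calculation, for means 60 and 180) in 13.4.2 and 13.7.
- If the 170 comes from a value above 325 mg for non-reactors, or from another dose scale, write that rule into 3.2 and 13.2 before unblinding and recompute the power on that basis.
- On the second route, write the PD2 rule for first-dose reactors, who have no previous dose, into the same sections. On the first route it is also needed before any floor above 0 is used to claim a smaller SD.
- Reword the phrase about the SD remaining true so that 42 is stated to apply to placebo only.

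The cost is protocol and SAP wording plus a short recalculation. With PD2 limited to 325 mg the sample size does not change; otherwise it should be confirmed after the recalculation.

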13.4.3 Supportive Analyses of the Primary Endpoint(s)/Outcome(s)

N/A

13.4.4 Analyses of Secondary and Other Endpoint(s)/Outcome(s)

Using a two-sided two-sample t-test for mean difference with unequal variance we will compare each secondary outcome (aspirin-induced fall in FEV_1 , aspirin-induced peak urinary LTE_4 and serum/nasal tryptase) separately on treatment with ifetroban or placebo. Based on our current internal clinical data:

- i. We estimate an average maximum aspirin-induced fall in FEV₁ of 14.6% with a standard deviation of 8.3. With 20 patients per treatment group, we will have 72% power to detect a 50% difference in the fall of FEV₁ at a 0.05 level of significance.
- ii. We estimate an average aspirin-induced peak urinary LTE₄ of 6.0 ng/mg Cr with a standard deviation of 3.9. With 20 patients per treatment group, we will have 74% power to detect a difference of 2.4 ng/mg Cr (or a 40% decrease in the rise in LTE₄) at a 0.05 level of significance.

We will compare each outcome (ifetroban-induced changes in baseline FEV₁, asthma control (ACQ), nasal symptoms (SNOT-22), FeNO and baseline LTE₄) separately after 4 weeks of treatment with ifetroban or placebo using a two-sided two-sample t-test. Based on our current internal clinical baseline data of 25 patients with AERD:

- iii. We estimate an average baseline FEV₁ of 92% predicted and a standard deviation of 9.8, we will have 78% power to detect a difference in FEV₁ of 6%, at a 0.05 level of significance.
- iv. We estimate an average baseline ACQ of 0.64 and a standard deviation of 0.54, we will have 82% power to detect a difference of 0.35 points, at a 0.05 level of significance. A fall in ACQ of 0.5 points is consistent with clinically significant improvement.³³
- v. We estimate an average baseline SNOT-22 score of 38 and a standard deviation of 14, we will have 86% power to detect a difference of 9 points, at a 0.05 level of significance. A fall in SNOT-22 score of 8.9 is consistent with clinically significant improvement.³⁴

We estimate an average baseline urinary LTE₄ of 0.37 ng/mg Cr and a standard deviation of 0.22, we will have 80% power to detect a difference of 0.14 ng/mg Cr (or a decrease in urinary LTE₄ of 30% from baseline, roughly half of the effect of zileuton,^{35,36} at a 0.05 level of significance.

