3.3. Secondary Outcomes

The secondary outcomes include the following:

- The severity of bronchoconstriction (measured by maximum percent fall in FEV₁) during the aspirin-induced reaction at Visit 2, compared between patients on placebo vs ifetroban.
- Increase in urinary and nasal levels of cysLTs during aspirin-induced reaction at Visit 2 from Visit 2 pre-aspirin levels, compared between patients on placebo vs ifetroban, as a proof-of-mechanism that TP receptor signaling in AERD drives cysLT overproduction.
- Change in levels of other urinary and nasal eicosanoids, and levels of plasma/serum and nasal tryptase, both from Visit 1 to Visit 2 prior to aspirin administration and also from Visit 2 prior to aspirin administration to during aspirin-induced reactions at Visit 2, compared between patients on placebo vs ifetroban.
- Change in numbers/percentages of activated platelets and platelet-leukocyte aggregates in the peripheral blood between Visit 1 and Visit 2 baseline (pre-aspirin administration) and Visit 2 baseline and during the aspirin-induced reaction at Visit 2, compared between patients on placebo vs ifetroban.

- Change in baseline (pre-aspirin administration) FEV₁, Asthma Control Questionnaire (ACQ), and Sino-Nasal Outcome Test (SNOT-22) at Visit 2 from Visit 1, compared between patients on placebo vs ifetroban.
- Change in Visit 2 baseline (pre-aspirin administration) levels of exhaled nitric oxide (FeNO) from Visit 1, compared between patients on placebo vs ifetroban.
- For each secondary endpoint above, which compares the aspirin-induced changes during the aspirin-induced reaction at Visit 2 for patients on placebo vs ifetroban, we will also analyze these changes with provocative aspirin dose as a covariate. We will treat provocative aspirin dose as level variable: in log scale, if the aspirin doses are 40.5, 81, 162, and 325, we will code the dose variable as dose 1, 2, 3 and 4 assume each increase in dose is linear.

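### Reaction LTE₄ is defined as an increase but tested as an untransformed, unadjusted peak; name one endpoint and adjust it for the pre-randomisation Visit 1 level

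*Combined protocol and SAP*

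**What the plan says.** Section 3.3 defines the outcome as "Increase in urinary and nasal levels of cysLTs during aspirin-induced reaction at Visit 2 from Visit 2 pre-aspirin levels", and item 2 of the synopsis secondary endpoints does the same for urinary and nasal LTE₄. Section 3.3 presents the comparison as the proof of mechanism for TP signalling driving cysteinyl leukotriene overproduction. It also plans a further analysis with provocative aspirin dose as a covariate.

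Section 13.4.4 names a different variable, "aspirin-induced peak urinary" LTE₄, and a single method for it, for the aspirin-induced fall in FEV₁ and for tryptase: "Using a two-sided two-sample t-test for mean difference with unequal variance we will compare each secondary outcome". The assumed peak is an average "of 6.0 ng/mg Cr with a standard deviation of 3.9". The sizing is "74% power to detect a difference of 2.4 ng/mg Cr" with 20 per group, glossed in brackets as "or a 40% decrease in the rise in" LTE₄, and tested "at a 0.05 level of significance". No transformation, baseline covariate, distribution or ifetroban-arm SD is given for LTE₄.

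**The concern.** A peak, a rise and a percentage fall are three different quantities, and the plan uses all three for one outcome. A reader of the final report could not tell which was prespecified. A difference of means in ng/mg Cr does not estimate a percentage fall.

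The comparison also makes no use of the Visit 1 urine and nasal samples, which sections 3.1 and 8.3 collect before treatment starts. With about 20 completers per arm and a coefficient of variation (CV) near 0.65, that may give up precision on the outcome that carries the mechanistic claim.

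**Working it through.** **Inputs from 13.4.4.** Peak mean 6.0, SD 3.9; resting mean 0.37, SD 0.22 (all ng/mg Cr); difference 2.4; 20 per arm; two-sided 0.05. The shape of the distribution, the ifetroban-arm SD and the correlation between Visit 1 and reaction levels are not given, so they are assumed and varied below.

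**The plan's own figure.** Two-sample t-test with equal SDs: noncentrality = 2.4 / (3.9 × √(2/20)) = 1.946 on 38 df, power 47.5%. If the ifetroban SD shrinks with its mean (0.6 × 3.9 = 2.34), power is 62.8%. Neither is the printed 74%. That discrepancy is a separate matter; the point here is the choice of endpoint and analysis.

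**Peak against rise.** 2.4 / 6.0 = 40% of the peak. The implied rise is 6.0 − 0.37 = 5.63, and 40% of it is 2.25. Cutting the rise by 40% gives a peak ratio of (0.37 + 0.6 × 5.63) / 6.0 = 0.625, not 0.60.

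**Why a log scale is worth considering.** The CVs are 0.22/0.37 = 0.59 and 3.9/6.0 = 0.65, although the means differ about 16-fold, so SD is roughly proportional to mean. Normal distributions with these moments would put 4.6% of resting values and 6.2% of peak values below zero.

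**Log step alone.** For lognormal data with CV 0.65 in both arms, the SD of the log is √ln(1 + 0.65²) = 0.594 and ln 0.6 = −0.511. Noncentrality is 0.511 / (0.594 × √0.1) = 2.72, power 75.5%. The raw Welch test on the same simulated data has about 68%. Other assumptions, with means 6.0 and 3.6 and placebo CV 0.65:

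| Shape, ifetroban CV | Raw Welch | Log | Log minus raw |
|---|---|---|---|
| Lognormal, 0.45 | 76.3% | 71.5% | −5 |
| Lognormal, 0.55 | 72% | 73.4% | +1.5 |
| Lognormal, 0.65 | 68% | 75.5% | +7 |
| Lognormal, 0.80 | 63.1% | 78.6% | +16 |
| Lognormal, 1.08 (equal raw SD) | 56.7% | 83.9% | +27 |
| Gamma, 0.45 | 72.6% | 51.1% | −21 |
| Gamma, 0.65 | 65.0% | 59.2% | −6 |
| Gamma, 1.08 (equal raw SD) | 51.1% | 78.0% | +27 |

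If the effect is a 40% cut in the rise (peak ratio 0.625), log-scale power in the lognormal equal-CV case falls to 68.5%.

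**Adjusting for the Visit 1 level.** The residual SD becomes SD × √(1 − ρ²). In the lognormal equal-CV case on the log scale:

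- ρ = 0.3: 0.594 × √0.91 = 0.566, power 79%
- ρ = 0.5: 0.594 × √0.75 = 0.514, power 86%
- ρ = 0.7: 0.594 × √0.51 = 0.424, power 96%

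The unadjusted figure is 75.5%. In simulations on raw and log scales, lognormal and gamma, with ifetroban CV from 0.45 to 0.80, adjustment added about 2–4, 7–12 and 17–26 points at ρ = 0.3, 0.5 and 0.7. At ρ = 0 it lost at most about 1 point. In the lognormal equal-raw-SD case, unadjusted log-scale power is already 84%, so less than 16 points remain to be gained.

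**A logged fold-rise is not equivalent.** In the lognormal equal-CV case, subtracting the log pre-aspirin level gives power of 49%, 64%, 78% and 94% at ρ = 0, 0.3, 0.5 and 0.7. It is worse than the unadjusted log peak when the correlation is low; using the baseline as a covariate avoids that loss.

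**The case against.** The planned test is valid: under a lognormal null with these moments, raw Welch rejects about 4.3% of the time, so this is a question of estimand and efficiency on a secondary outcome. That stands.

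The evidence for a particular shape is thin. The negative tail rules out exact normality but does not identify a lognormal, and a gamma with the same CV reverses the sign of the gain. That stands too. A reader might infer that taking logs buys about 7 points of power for nothing and exactly matches the stated effect. The documents do not support this. The 7 points need lognormal data with equal CVs, neither of which is stated. The printed 2.4 is an absolute difference equal to 40% of the peak, not of the rise. The geometric mean ratio equals the ratio of means only if the CVs agree: at a lognormal ifetroban CV of 0.45 it would be 0.65 rather than 0.60.

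A reaction level adjusted for Visit 1 also mixes any four-week effect on resting LTE₄, which 13.4.4 tests separately, with blunting of the acute reaction. That is a fair criticism, and it is why the rise should be reported as well.

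Finally, section 3.3 already has a covariate analysis. But provocative dose is observed after randomisation and may itself respond to treatment, so it adds to a baseline adjustment and does not replace one.

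**Conclusion.** The mismatch between increase and peak, and the description of 40% of the peak as 40% of the rise, are on the page and need no assumption. The dependable improvement is adjustment for the Visit 1 level. Its size depends on a correlation the documents do not give, but the possible loss is about 1 point.

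The log scale is justified mainly because the effect is discussed as a percentage and SD roughly tracks the mean. It should not be justified by a promised power gain, since even the sign of that gain depends on the distribution and the ifetroban-arm spread.

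**What to change.** - Define one reaction-phase LTE₄ endpoint and word it identically in the synopsis, 3.3 and 13.4.4. State which reaction sample or samples it uses, because 3.1 lists three collection times and 8.3 one. Restate the target effect on that endpoint, correcting either the 2.4 or the 40%-of-the-rise description.
- Analyse it, together with tryptase and other mediators that have a Visit 1 sample, in a linear model with arm and the Visit 1 level. Keep the provocative-dose model as the additional analysis.
- Before unblinding, check the shape in the internal LTE₄ data. If it supports a log scale, prespecify the log model and report the ifetroban/placebo geometric mean ratio with its 95% CI.
- Report the rise from the Visit 2 pre-aspirin level alongside.

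The cost is a change to the wording of a secondary endpoint and its analysis, with no new samples. A log analysis also needs a rule for values below detection and changes the estimand to a ratio of geometric means.

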Secondary Endpoint(s)	
1. Severity of bronchoconstriction (as measured by maximum fall in FEV₁ during the aspirin-induced reaction) during the aspirin-induced reaction at Visit 2, compared between patients on placebo vs ifetroban, with the changes also analyzed with provocative aspirin dose as a covariate.
 
2. Increase of urinary, and nasal lavage levels of LTE₄ during aspirin-induced reaction from Visit 2 pre-aspirin levels, compared between patients on placebo vs ifetroban, with the changes also analyzed with provocative aspirin dose as a covariate.
 
3. Change from Visit 1 in baseline FEV₁, Asthma Control Questionnaire (ACQ), and Sino-Nasal Outcome Test (SNOT-22) at Visit 2, compared between patients on placebo vs ifetroban.
 
4. Change in levels of other urinary, and nasal eicosanoids, and levels of plasma/serum and nasal tryptase, from Visit 1 to Visit 2 pre-aspirin challenge and Visit 2 pre-aspirin to during the aspirin-induced reaction at Visit 2, compared between patients on placebo vs ifetroban, with the changes also analyzed with provocative aspirin dose as a covariate.
 
5. Change from Visit 1 in baseline exhaled nitric oxide (FeNO) levels at Visit 2, compared between patients on placebo vs ifetroban.

	6. Change in numbers/percentages of activated platelets and platelet-leukocyte aggregates in the peripheral blood from Visit 1 to Visit 2 baseline (pre-aspirin administration) and during the aspirin-induced reaction at Visit 2 from Visit 2 baseline, compared between patients on placebo vs ifetroban, with the changes also analyzed with provocative aspirin dose as a covariate.
Accrual Objective	50 subjects
Study Duration	36 months
Treatment Description	Ifetroban and aspirin
Inclusion Criteria	
 1. History of AERD, defined as meeting the diagnostic triad with: 
 1. History of physician-diagnosed asthma and 2. History of physician-diagnosed nasal polyposis and 3. History of pathognomonic reactions aspirin or other nonselective COX inhibitors. 2. Stable asthma (post-bronchodilator FEV₁ of ≥70%, no glucocorticoid burst for at least 2 weeks prior to Visit 1, and no hospitalizations or ER visits for asthma for at least the prior 6 months) 3. Age between 18 and 70 years 4. No current smoking (not more than one instance of smoking in the last 3 months) 5. Non-pregnant

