13.4.5 Analyses of Exploratory Endpoint(s)/Outcome(s)

Nasal fluid IL-33 and tryptase levels are expected to increase during aspirin-induced reactions and those increases will be compared between patients on ifetroban vs. placebo to determine if ifetroban treatment blunts the aspirin-induced increases. The IL-33 and tryptase levels will also be correlated to clinical symptoms (TNSS and fall in FEV1). We will measure the incremental increase in platelet or mast cell-derived chemokines in the nasal fluid during aspirin-induced reactions for patients on ifetroban vs. placebo and determine if those increases are blunted by ifetroban or correlate with the increase in nasal eicosanoids during reaction.

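### Section 13.4.4 analyses and sizes urinary LTE4 on the reaction peak and leaves the tryptase variable open, while the endpoints are changes from the Visit 2 pre-aspirin value

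*Combined protocol and SAP*

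**What the plan says.** **Endpoint definitions.** Synopsis secondary endpoint 2 takes the LTE4 endpoint, in urine and nasal lavage, as an increase during the reaction "from Visit 2 pre-aspirin levels, compared between patients on placebo vs ifetroban, with the changes also analyzed with provocative aspirin dose as a covariate". Section 3.3 says the same of cysteinyl leukotrienes: "during aspirin-induced reaction at Visit 2 from Visit 2 pre-aspirin levels, compared between patients on placebo vs ifetroban", there described as proof of mechanism. Synopsis endpoint 4 and the matching item in 3.3 define the reaction-phase outcome for other eicosanoids and for plasma/serum and nasal tryptase as the change from the Visit 2 pre-aspirin sample to the reaction.

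**Analysis.** Section 13.4.4 states: "Using a two-sided two-sample t-test for mean difference with unequal variance we will compare each secondary outcome". Its bracketed list names the aspirin-induced peak of urinary LTE4 together with serum/nasal tryptase. The sizing item reads "We estimate an average aspirin-induced peak urinary" LTE4 "of 6.0 ng/mg Cr with a standard deviation of 3.9". It continues "With 20 patients per treatment group, we will have 74% power to detect a difference of 2.4 ng/mg Cr", and glosses that difference as "or a 40% decrease in the rise in" LTE4.

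**Nasal tryptase elsewhere.** Section 13.4.5 covers IL-33 and tryptase in nasal fluid and says "those increases will be compared between patients on ifetroban vs. placebo".

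**Adjustment.** The only covariate planned for reaction-phase outcomes is provocative aspirin dose (synopsis; 3.3). The t-test in 13.4.4 is unadjusted.

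**The concern.** A peak level and a rise from a pre-challenge value are different variables. Elsewhere in 13.4.4 a change is called a change (the fall in FEV1, the ifetroban-induced changes in baseline measures), so the word peak reads naturally as a level. On that reading, the test that is named and sized is not a test of the endpoint in the synopsis and 3.3.

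The distinction bears on the mechanism question. The plan also tests whether four weeks of ifetroban lowers basal urinary LTE4. If it does, part of any difference in peak comes from a lower starting point rather than a blunted surge, and the rise is the variable that separates the two.

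If the choice stays open, the analyst could settle on peak or rise after seeing the data. What counts as the reaction value is unsettled as well. Section 3.1 collects urine and nasal samples at onset, 90 minutes and 3 hours, whereas the Visit 2 list in 8.3 gives only 90 minutes after onset. Under 3.1 a peak is the largest of three values; under 8.3 it is a single value.

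**Working it through.** **Inputs (all from 13.4.4).** Peak urinary LTE4: mean 6.0, SD 3.9 ng/mg Cr. Target difference: 2.4. Sample size: 20 per arm. Test: two-sided, alpha 0.05. Basal urinary LTE4: mean 0.37, SD 0.22. Basal difference the plan is powered for: 0.14. The correlation ρ between pre-aspirin and peak values is not given, so I take 0 to 1. I assume that the basal figures describe the Visit 2 pre-aspirin sample and that both arms share one SD.

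**1. The plan's own figure.** Standardised difference = 2.4/3.9 = 0.615. For the two-sample test, noncentrality = 0.615 × √(20/2) = 1.95, which gives 47.5% power by the t distribution with 38 df (49.4% by normal approximation). The stated 74% is not reproduced. A paired or one-sample t-test with n = 20 has noncentrality 0.615 × √20 = 2.75 and gives 74.2%. That matches the stated figure, and section 13.1 still calls the trial a crossover. The unequal-variance test comes within two points of 74% only if the ifetroban SD is about 1.0 or less (72.1% at 1.0, 73.7% at 0.5), which the plan does not state.

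**2. Peak or rise?** 0.40 × 6.0 = 2.4, so the target is 40% of the peak. Mean rise = 6.0 − 0.37 = 5.63. 40% of the rise = 0.40 × 5.63 = 2.25, and 2.4/5.63 = 42.6%.

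**3. Spread and power on the rise.** SD of rise = √(3.9² + 0.22² − 2ρ × 3.9 × 0.22). Power is for the two-sample t-test with 20 per arm.

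| ρ | SD of rise | Power for 2.25 | Power for 2.4 | n per arm for 74% at 2.25 |
|---|---|---|---|---|
| 0 | 3.91 | 42.8% | 47.4% | 42 |
| 0.5 | 3.79 | 44.8% | 49.6% | 40 |
| 0.8 | 3.73 | 46.1% | 51.0% | 39 |
| 1 | 3.68 | 47.1% | 52.0% | 38 |

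**4. How much basal level enters the peak.** Share of variance: 0.22²/3.9² = 0.0484/15.21 = 0.3%. Share of the target if the whole planned basal effect occurred: 0.14/2.4 = 5.8%.

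**5. Tryptase and nasal LTE4.** The documents give no mean, SD or correlation for these, so none of the above can be repeated for them.

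**The case against.** The strongest defence is that peak is loose shorthand. Section 13.4.4 says it compares each secondary outcome, 13.2 refers the reader to 3.3 and 3.4 for what those are, and the LTE4 item itself speaks of the rise. This has force: the plan is internally inconsistent rather than clearly committed to the level. It does not settle the matter, because the mean, SD and target difference are all those of the peak.

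The defence also limits what may be concluded. A reader might infer any of the following, and the documents do not support them:

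- **Tryptase is tested as a level, so nasal tryptase has two conflicting analyses.** Section 13.4.4 names tryptase without saying level, peak or change, and 13.4.5 compares nasal increases. The two sections are unreconciled, not contradictory. Only for serum/plasma tryptase does section 13 never say that the increase is analysed.
- **The pre-aspirin sample is collected but not used.** This is true only of the reaction-phase test in 13.4.4. Basal LTE4 after four weeks is compared there as its own outcome, and 13.4.5 works with increases.
- **A lower peak may be mainly a lower starting level, or basal imbalance biases the comparison.** With a peak averaging 6.0 against a basal 0.37, the first cannot hold for urinary LTE4. Allocation is randomised, so chance basal differences add noise rather than bias.
- **Analysing the increase would raise power for tryptase.** That depends on SDs and a correlation that the documents do not give, and the change could go either way.

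**Conclusion.** The point holds as a mismatch between endpoint and analysis. The synopsis and 3.3 define a change from the Visit 2 pre-aspirin value; 13.4.4 names and sizes the urinary LTE4 peak, describes the target as a share of the rise, and leaves the tryptase variable unstated.

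For urinary LTE4 the numerical consequence is small. Moving from peak to rise takes the SD from 3.9 to between 3.68 and 3.91, changes power for 2.4 from 47.5% to 47–52%, and turns a true 40% reduction of the rise into 2.25. These figures rest on the assumptions listed with the inputs. For tryptase and nasal LTE4 the size is unknown.

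The shortfall from 74% to about 47% is a separate and larger problem in the same item. It comes from the test used in the calculation, not from the choice of peak or rise, but it has to be corrected when the item is re-sized. This is a change the sponsor should make; it concerns secondary endpoints and does not touch the primary analysis.

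**What to change.** 1. In 13.4.4, define the analysed variable for reaction-phase LTE4 and for serum/plasma and nasal tryptase as the reaction value minus the Visit 2 pre-aspirin value.
2. Fix the reaction value in advance, as one named time point or as the maximum over named times, and reconcile the sampling times in 3.1 and 8.3 so that it can be computed for every participant.
3. Keep the peak as a supportive summary.
4. Use the same variable for nasal tryptase in 13.4.4 and 13.4.5.
5. Restate the LTE4 target and power on the increase for the planned two-sample test with 20 per arm: about 43–47% for 2.25, or 47–52% for 2.4. Replace the values derived here with the mean and SD of the observed increase from the sponsor's internal data if available.

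**Cost.** Mainly a change of wording, since the pre-aspirin and 90-minute samples are in both descriptions of Visit 2. There are two downsides. The stated power becomes less favourable. Some precision is also lost for any analyte whose pre-aspirin and reaction values are weakly correlated: the increase is more variable than the level when ρ is below SD(pre)/(2 × SD(reaction)). For urinary LTE4 that threshold is 0.22/(2 × 3.9) = 0.03, so the loss there is negligible; for tryptase it is unknown.
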